Treatment for pediatric acute myeloid leukemia (AML) or myelodysplastic syndrome (MDS) involves intensive chemotherapy regimens that result in periods of profound neutropenia leaving patients susceptible to severe infectious complications. Infectious complications are the leading cause of treatment related mortality among AML and MDS patients, but there are little clinical data to inform whether management of neutropenia post AML chemotherapy should occur in an outpatient or inpatient setting. Further, no studies have been conducted that assess the impact of neutropenia management strategy on the quality of life of pediatric patients with AML/MDS and their caregivers.

Objectives:

The primary objective of this study is to compare patient and caregiver quality of life and other patient-centered outcomes (PCO) for inpatient versus outpatient management of neutropenia in children with AML or MDS receiving standard intensive AML frontline chemotherapy.

Study Design:

This is a prospective observational cohort study.

Setting/Participants:

[figure not shown]
Participants will be patients less than 19 years of age at their initial AML or MDS diagnosis (and their caregivers) receiving or having received frontline AML chemotherapy from fifteen participating pediatric hospitals across the United States (US). Due to the nature of the survey collected data, only dyads who are English/Spanish literate will be eligible. We expect to identify 139 patient-caregiver dyads, of which we anticipate that approximately 118 will consent to participate over the study period to compare patient- and caregiver-identified outcomes of neutropenia management in the outpatient and inpatient settings.

Study Interventions and Measures:

There is no study intervention. Main outcomes include scores on health-related quality of life surveys, as well as additional patient- and caregiver- identified outcomes.

TABLE 1: SCHEDULE OF STUDY PROCEDURES

Study Phase	Screening	Study Visits	
Visit Number		1	2
Informed Consent/Assent	X		
Review inclusion/exclusion criteria	X		
Baseline PedsQL™		X	
Demographic survey		X	
Demographic survey II		X	
Follow-up PedsQL™			X
PCO survey			X
Financial toxicity survey		X	X

FIGURE 1: STUDY DIAGRAM

1 BACKGROUND INFORMATION AND RATIONALE

1.1 Introduction

Acute myeloid leukemia (AML) is the second most common pediatric hematologic malignancy with approximately 600 new cases per year among patients under 20 years of age. Although AML accounts for only about 20% of leukemias in children, it is responsible for more than half of pediatric leukemia deaths (1). The prognosis of children with AML has improved greatly over the past 30 years (2, 3, 4), attributable largely to the intensification and standardization of chemotherapy regimens.

All pediatric patients with newly diagnosed AML receive multiple consecutive courses of intensive myelosuppressive chemotherapy aimed to attain complete remission (induction) and to prevent relapse (intensification) (5). Each regimen is followed by a period of prolonged severe neutropenia during which patients are at high risk for infection and hemorrhage. Previous reports have found that 57-80% of febrile neutropenia episodes among pediatric AML patients are compromised by at least one microbiologically documented infection (6, 7) with bacteremia constituting the most prevalent infection (8). These infectious complications remain a major cause of therapy-associated morbidity and mortality in children with AML (9, 10).

Recently published pediatric neutropenia guidelines make no specific recommendations regarding discharge from hospital after chemotherapy for AML because “there are no validated schemas for defining those patients at high-risk of developing complications of fever and neutropenia” (11). As a result, clinicians are left to decide whether to keep a child in the hospital until the neutropenia resolves (on average 35 days) or discharge a child to outpatient management within a few days of chemotherapy completion with instructions to return if symptoms of infection develop. Physicians that elect to observe patients with neutropenia in the hospital do so under the assumption that hospital observation will reduce the risk of serious infection and thereby reduce delays in starting the next course of chemotherapy. Furthermore, this approach assumes that the potential reduction in infection outweighs the potential negative consequences of a prolonged inpatient stay—namely reduced quality of life, increased exposure to multi-resistant nosocomial infections, and increased healthcare cost. There is documented variation in practice across Children’s Oncology Group (COG) institutions on inpatient versus outpatient management of neutropenia with approximately 60% of COG institutions reporting a policy to always keep patients hospitalized during severely neutropenic periods and the remaining 40% of hospitals reporting a policy of home management some or all of the time (12, 13). This variation in practice highlights the need for additional data on clinician-centered and patient-centered outcomes to appropriately guide the management of neutropenia in pediatric AML patients.

Myelodysplastic syndromes (MDSs) are a rare heterogenous group of hemopoietic clonal disorders characterized by ineffective hemopoiesis and frequent evolution to leukemia. Children with clinical and morphological features of MDS but with the cytogenetic features typical of AML are often treated with same intensive frontline chemotherapy used to treat AML. (38) Thus, questions regarding clinician-centered and patient-centered outcomes in

relation to outpatient versus inpatient management of neutropenia would apply equally to such patients.

1.2 Relevant Literature and Data

The limited literature on the clinical consequences of outpatient versus inpatient management of neutropenia in AML is focused on the experience of adult patients. Adult patients discharged early to outpatient supportive care consistently had shorter cumulative lengths of stay than inpatients (14-21). Additionally, early discharge of adult AML patients receiving chemotherapy has been associated with fewer and shorter febrile episodes (18, 22), a better response to first line antibiotics, and shorter duration of intravenous antibiotic administration (16, 18, 21, 22). While these adult studies provide some reassurance that outpatient management may be safe and feasible they are limited as most included data from only a single institution, had very small sample sizes, or lacked an appropriate inpatient reference population. Furthermore, it is not appropriate to extrapolate these adult findings to pediatric patients as the risk profile for children may be much different.

The published literature with respect to outpatient management of neutropenia in pediatric AML is limited to a single study of only 13 patients from one hospital, which found similar rates of relapse and mortality for outpatient versus inpatient management of neutropenia (23). In our own preliminary analyses based on administrative resource utilization data from 43 free-standing children's hospitals in the US, we found that patients who were discharged early to outpatient management following AML induction and intensification chemotherapy courses incurred fewer cumulative days of hospitalization, but were frequently readmitted and had higher rates of antibiotic, vasopressor, and supplemental oxygen utilization than patients who remained inpatient during the entirety of their neutropenia. In the absence of clinical data and laboratory confirmation, it is unclear whether these observed increases in resource utilization are an accurate proxy for a greater incidence of infection or more severe infection in the early discharge patients.

Decisions regarding supportive care strategies are intended not only to improve clinical outcomes but also to impact patient quality of life outcomes, such as minimizing the psychological, social and spiritual challenges related to therapy (24). Thus, it is imperative to determine the impact of a chosen neutropenia management strategy on the child's quality of life and interactions with his or her broader social environment, including impact on the family. There is a dearth of literature on child and caregiver (parent/guardian) perspectives on outpatient versus inpatient management of neutropenia (25, 26) or the impact of neutropenia management strategy on quality of life (27) in pediatric cancer patients. The one qualitative study on parent preferences for neutropenia management in pediatric cancer found that most respondents preferred hospital-based treatment once a patient had developed a fever during neutropenia (25). Factors that influenced parent preference for febrile neutropenia management included convenience and disruptiveness to family life, concerns about the child's physical health (including infection), and concerns about the child's emotional wellbeing. While this study was a good first step in identifying PCO for febrile neutropenia management in pediatric cancer it has some notable limitations: it was conducted at one center in Canada, it only included parent perspectives on febrile

neutropenia management and not management of neutropenia prior to fever onset, children were not interviewed, and it involved the elicitation of parent preferences via hypothetical scenarios versus more in-depth study of the actual experience of neutropenia management in the hospital or the home.

There are no studies evaluating clinician-centered and patient-centered outcomes in relation to outpatient versus inpatient management of neutropenia among MDS patients treated with standard intensive AML frontline chemotherapy. However, these patients suffer the same severe prolonged neutropenia as similarly treated AML patients and as such, assessments of patient quality of life and other family-centered outcomes for outpatient versus inpatient management of neutropenia would be equally informative to decisions on their supportive care strategies.

In order to appropriately inform the decision for outpatient versus inpatient management of neutropenia associated with pediatric AML chemotherapy, a comprehensive study that considers pertinent clinical, patient and caregiver centered outcomes is necessary. Given that infectious complications are the leading cause of treatment-related mortality among AML patients (28) and among MDS patients (39, 40), identifying such a neutropenia management strategy that leads to the best clinician and patient/caregiver identified outcomes will have a substantial impact on care of these patients.

1.3 Compliance Statement

This study will be conducted in full accordance with all applicable Children's Hospital of Philadelphia Research Policies and Procedures and all applicable Federal and state laws and regulations including 45 CFR 46. All episodes of noncompliance will be documented.

The investigators will perform the study in accordance with this protocol, will obtain consent and assent, and will report unanticipated problems involving risks to subjects or others in accordance with The Children's Hospital of Philadelphia IRB Policies and Procedures and all federal requirements. Collection, recording, and reporting of data will be accurate and will ensure the privacy, health, and welfare of research subjects during and after the study.

2 STUDY OBJECTIVES

The purpose of this study is to establish important comparative effectiveness data on patient-directed outcomes for outpatient versus inpatient management of AML neutropenia or MDS in individuals receiving standard AML frontline chemotherapy.

2.1 Objectives

The primary objective of this study is to compare patient and caregiver reported quality of life and other PCO (established through previous qualitative interviews conducted by a medical sociologist at CHOP) for inpatient versus outpatient management of neutropenia in children with AML or MDS receiving standard intensive AML frontline chemotherapy.

3 INVESTIGATIONAL PLAN

3.1 General Schema of Study Design

This prospective observational cohort study will evaluate patient- and caregiver-directed outcomes of inpatient versus outpatient management of neutropenia following chemotherapy in children with AML or MDS.

3.2 Study Duration, Enrollment and Number of Sites

This study plans to include patients and their caregivers who are undergoing frontline chemotherapy starting June 1, 2016 or after.

3.3 Total Number of Study Sites/Total Number of Subjects Projected

3.3.1 Duration of Study Participation

Eligible patients will be approached for consent at any time from initial AML or MDS diagnosis through the last day of chemotherapy in the frontline treatment course under study. The maximum duration of enrollment is from the initiation of their current chemotherapy course until the last day of their subsequent chemotherapy course. This duration is estimated to be approximately 30-40 days.

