3.4 Study Population

The study population will include all AML and MDS patients who are receiving a planned frontline chemotherapy course at any of the fifteen pediatric institutions across the US starting June 1, 2016. Patients discharged within 3 days after chemotherapy completion will be categorized as 'early discharge' to outpatient management during neutropenia. Patients remaining in the hospital more than 3 days after chemotherapy completion will be categorized as inpatient management.

Caregivers of these patients will also be included.

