We will utilize linear mixed effect models to test the association between neutropenia management strategy and the PedsQL™ total score. Specifically, the two repeated measures of the PedsQL™ total score will be the outcome and regressed on time, group (outpatient versus inpatient) and interaction between time and group will be the fixed effects, and a subject level random effect will be included to account for the potential correlations between the repeated measures. Such mixed models are more powerful than ANCOVA or analysis of change scores, and they benefit from the added power arising from any correlation of repeated measures over time. A significant group by time interaction will suggest that the change of PedsQL™ is different between the two groups. Adjustment for differences in covariates across neutropenia management groups will be accomplished through the propensity score outlined above, and by controlling for confounding of any remaining unbalanced potential confounders. Secondary analyses will be performed for the cancer and fatigue modules as well as for the physical and psychosocial subscales of the PedsQL™.

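### Because children may enter in any frontline course, a later-course Visit 1 may carry earlier management, and an unequal first-course share would bias the group-by-time estimate

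*Combined protocol and SAP*

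**What the plan says.** Entry is not tied to a particular course. Under section 3.3.1 patients are "approached for consent at any time from initial AML or MDS diagnosis through the last day of chemotherapy in the frontline treatment course under study". Section 3.4 takes all patients "receiving a planned frontline chemotherapy course at any of the fifteen pediatric institutions", and the abstract describes participants as "receiving or having received frontline AML chemotherapy". Section 1.1 says that newly diagnosed children "receive multiple consecutive courses of intensive myelosuppressive chemotherapy", with a long neutropenic period after each.

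Visit 1 falls before the last chemotherapy day of the studied course (section 4.3). Visit 2 may be as late as the last chemotherapy day of the next course (section 4.4). Early discharge is defined course by course (Definitions).

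The primary model in section 6.3.1 has time, group and their interaction, with a subject random effect: "A significant group by time interaction will suggest that the change of PedsQL™ is different between the two groups". Adjustment is through propensity quintiles plus any covariates still unbalanced. Section 5.1.2 lists course number and the admission and chemotherapy dates among the abstracted data. No section names course number or prior-course strategy as a covariate, stratum or effect modifier, and no first-course analysis is planned.

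**The concern.** Two separate things can go wrong when first-course and later-course children are pooled.

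1. **Carry-over.** The window in which the effect of one course is measured (Visit 2) overlaps the window in which the baseline of the next course is measured (Visit 1). An effect that can be seen at Visit 2 can therefore be present in the Visit 1 score of a child who enters one course later. The group-by-time term removes whatever group difference exists at Visit 1. If children tend to be managed the same way from course to course, part of the effect may be removed with it, and a null result could be misread as no effect of strategy.

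2. **Mix of courses.** A first-course child has Visit 1 soon after diagnosis, so the change to Visit 2 also contains adjustment to the diagnosis and response to induction. If the share of first-course children differs between outpatients and inpatients, that natural change enters the interaction as bias, in either direction.

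**Working it through.** **The plan's own figure.** Section 6.4 gives 47 outpatients and 71 inpatients, SD 20, alpha 0.05, and 80% power for 15.0 points (correlation 0) or 6.8 points (correlation 0.8). With two groups and two visits, the test is a two-sample t test on change scores.

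- SD of change = 20·√(2(1 − ρ)) = 28.28 at ρ = 0 and 12.65 at ρ = 0.8.
- Two-sided power from the noncentral t is 79.9% for 15.0 points and 80.9% for 6.8 points. The stated power reproduces. It assumes that the whole effect appears as change within the studied course.

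**Carry-over.** The documents do not give the following quantities, so all are assumed, with q and s taken as equal in the two groups:

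- q = share entering after the first course
- s = share of those whose previous strategy was the same as the current one
- c = fraction of the effect E still present at Visit 1

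At Visit 1 the mean carry-over is E·c·q·s in current outpatients and E·c·q·(1 − s) in current inpatients, a difference of E·c·q·(2s − 1). If the effect is a level that does not add up by course, the Visit 2 difference is E. The expected interaction is then E·[1 − c·q·(2s − 1)].

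With E = 6.8, ρ = 0.8 and q = 0.5, compared with 4,000 simulated studies per scenario:

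| Scenario | Factor | Expected points | Simulated points | Simulated power |
|---|---|---|---|---|
| c = 1, s = 1 | 1 − 0.5 = 0.50 | 3.4 | 3.5 | 30% |
| c = 1, s = 0.8 | 1 − 0.5·0.6 = 0.70 | 4.8 | 4.8 | 50% |
| c = 1, s = 0.5 | 1 − 0 = 1.00 | 6.8 | 6.8 | 77% |
| Effects add up by course | 1.00 | 6.8 | 6.8 | 80–81% |

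A middle case is q = 0.5, c = 0.5, s = 1. The factor is 1 − 0.25 = 0.75, so 15.0 becomes 11.25 points and 6.8 becomes 5.1. Power is 56% at ρ = 0 and 57% at ρ = 0.8. The true effect needed for 80% power rises to 20.0 or 9.0 points, and the sample size would have to be 1/0.75² = 1.78 times as large.

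**Mix of courses.** Suppose that first-course children change by 10 points more than later-course children for reasons unrelated to strategy, and that they make up 40% of outpatients and 60% of inpatients (all assumed). With no strategy effect at all, the interaction is 10·(0.40 − 0.60) = −2.0 points.

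**Does the planned adjustment remove it?** With both visits complete, the group-by-time estimate is the difference in mean within-child change. A covariate that is constant within a child and enters only as a main effect shifts both of that child's scores equally and cancels from the change. Propensity strata or course number entered that way leave the interaction estimate unchanged. A course-by-time term lets natural change differ by course, and it removes the bias.

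**First-course children alone.** If half the sample is first-course (24 versus 36), power is 51% for 15.0 points at ρ = 0 and 52% for 6.8 points at ρ = 0.8.

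**The case against.** The strongest reply is that the loss from carry-over is conjecture. A reader might infer that a later-course baseline does already contain the effect of the same strategy, and that the test is therefore biased toward no difference. The documents do not support that. The evidence on persistence is a survey of institutions, "approximately 60% of COG institutions reporting a policy to always keep patients hospitalized during severely neutropenic periods", with the rest using home management some or all of the time. It does not describe these fifteen sites or individual children. Choosing sites for variation in primary strategy (section 3.3.2) does not fix one strategy per child. The later-entry share is not given. If previous strategy is unrelated to current strategy, or effects add up by course, nothing is lost on average. This part of the reply stands.

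It is also tempting to multiply carry-over by the share of children with the same earlier strategy and stop there. That ignores children who switched, whose carry-over works the other way. At q = 0.5, s = 0.8, c = 1 the shortcut gives 6.8·(1 − 0.5·0.8) = 4.1 points, against the correct 4.8.

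Second, exposure is defined per course and the test concerns change, so removing the Visit 1 difference may be intended. That is a fair reading, but the objective in section 2.1 compares the strategies without restricting the question to one course's further change.

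Third, course number is abstracted and could be selected into the propensity score, or adjusted for as a remaining imbalance. It could, but section 6.3.1 does not say how the quintiles enter the mixed model. If they enter as main effects, the mix bias remains. A stratum-by-stratum comparison of change could reduce it, to the extent that the score captures course.

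**Conclusion.** The point holds in conditional form. Open entry, the overlapping visit windows and the removal of any Visit 1 difference come from the documents. Attenuation is possible but not established. It ranges from none (s = 0.5, or effects that add up) to a quarter of the effect at q = 0.5, c = 0.5, s = 1, and to half if carry-over is also complete. The base of 6.8 points is the plan's detectable difference at its most favourable correlation, not an expected effect.

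The mix bias does not depend on carry-over. It needs a first-course share that differs between groups and a natural change that differs by course. The documents give neither size; the −2.0 points above is an illustration. The plan as written does not ensure protection against it, and the data needed are already collected. A null primary result would not exclude a cumulative effect over several courses.

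**What to change.** In section 6.3.1:

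1. Force first versus later course, from the abstracted course number, and its interaction with time into the primary model, whatever the bivariate screening shows.
2. State that the propensity strata enter with their time interactions as well as their main effects.
3. State that the primary estimate is the change over the studied course given earlier management, and that a null result does not exclude a cumulative effect.

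As supportive analyses only:

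4. Report the group-by-time estimate in first-course children. Do not widen this subset to later-course children who switched strategy: their baseline may carry the opposite effect, which would inflate the estimate.
5. Where earlier-course admission, discharge and chemotherapy dates are held, describe prior-course strategy by group.

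Items 1 and 2 address the mix of courses; they do not restore an effect already carried into Visit 1. Items 3 to 5 address how that possibility is interpreted.

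The cost is SAP wording and one derived variable. The course terms use two degrees of freedom. Five strata use eight (four main effects and four time interactions), of which the four main effects would be present anyway if the strata enter as main effects. The first-course estimate will have a wide interval, and some sites may need to supply earlier-course dates for item 5. Visits and eligibility do not change.
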